2.5.2 Statistical hypothesis, model, and method of analysis

Adverse events will be summarized with descriptive statistics for the Safety Set.

The number and percentage of patients who reported treatment emergent adverse events will be summarized by primary system organ class, preferred term for

- All adverse events
- All adverse events by time at onset (≤ 12 weeks, $> 12 - \leq 26$ weeks, > 26 weeks)
- Serious adverse events
- Adverse events by maximum severity
- Adverse events suspected to be related to study drug
- Adverse events leading to permanent study drug discontinuation
- Adverse events of special interest

All adverse events including asthma exacerbations, coded with MedDRA using the most actual version at the time of database lock, will be listed.

Unless otherwise specified, primary system organ classes will be sorted alphabetically and, within each primary system organ class, the preferred terms will be sorted in descending order of frequency. If a patient reported more than one adverse event with the same preferred term, the adverse event will be counted only once. If a patient reported more than one adverse event within the same primary system organ class, the patient will be counted only once at the system organ class level.

In addition, the most frequent adverse events will be presented by preferred term in descending order of frequency.

For AEs by maximum severity, missing severity will be assumed to be severe in the summary table.

A composite endpoint of serious asthma outcomes is defined as a) asthma-related hospitalization, b) asthma-related intubation, or c) asthma-related death. All serious asthma outcomes and deaths occurring from the treatment epoch until the 30 days after permanent discontinuation of study drug will be adjudicated by an independent external committee to determine their asthma relatedness.

The composite endpoint as well as each single component of it will be analyzed for the number of patients with the event, the time to event and the annual rate of events.

The Compound Case Retrieval Strategy (CRS) will be used to determine the MedDRA search criteria to be used to identify events of special interest. The most recent list of adverse events of special interest at the time of database lock will be used.

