### **5.5.4 Instructions for prescribing and taking study treatment**

The investigator should promote compliance by instructing the patient to take the study treatment ([Section 5.1](#)) exactly as prescribed and by stating that compliance is necessary for the patient's safety and the validity of the study. The patient should be instructed to contact the investigator if he/she is unable for any reason to take the study treatment as prescribed.

At Visit 1 all patients will be instructed how to use a pMDI to administer rescue salbutamol correctly. At Visit 99 all patients will be fully trained in the correct use of the Concept1 to administer QMF149. Patients who are unable to use Concept1 correctly at Visit 99 will not be eligible to enter the treatment epoch. For this training purpose, training kits will be supplied to the investigator site. At each clinic visit the investigator should check the patient's use of the inhalational devices to ensure that they are using each device correctly. Additional device training should be provided if required.

Starting at Visit 101, all eligible patients will be instructed to take QMF149 150/320 µg via Concept1 once daily in the evening at approximately the same time of day. Patients will be instructed to rinse their mouth (e.g., 2 times with approximately 30 mL water) after inhalation of QMF149. Water used for mouth rinsing should be spat out and should NOT be swallowed.

The study treatment can be taken without regard to sleep, meals, and other activities. On days of scheduled clinic visits, patients should take QMF149 at the clinic (approximately between 4:00 to 8:00 pm) under the supervision of investigator or his/her delegate.

The duration of treatment epoch is 52 weeks, with the last dose of study treatment occurring in the evening of Day 365 (Visit 111).

All kits of investigational drug assigned by the IRT will be recorded in the IRT. All used and unused study medication/packaging must be returned by the patient at each study visit and/or at the time of discontinuation.

All dosages prescribed and dispensed to the patient and all dose changes during the study must be recorded on the Dosage Administration Record CRF.

If any faults are identified with either the device and/or the blisters, these should be returned to Novartis Drug Supply Management with the completed Device Return Form. The forms will be supplied to each investigator site by the Field Monitor.

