2.4 Treatments (study treatment, rescue medication, concomitant therapies, compliance)

2.4.1 Study treatment / compliance

Study drug administration and concomitant medication data will be listed and summarized using the Safety Set.

The duration of exposure and the number of patients who completed the study medication and who discontinued from the study medication will be summarized. Duration of exposure to study treatment will be calculated as the number of days starting from the first dose date up to and inclusive the last dose date. The duration of exposure will be summarized for the Safety Set as a continuous variable with the standard descriptive statistics. In addition, the duration of exposure will be summarized with total patient years and the number (%) of patients who were exposed to study drug for each 1 - 29 days, 30 - 86 days, 87 - 183 days, 184 - 254 days, 255 - 365 days, and > 365 days. The number of patients who completed the 52-week study treatment and who discontinued prematurely will be shown including the reasons for discontinuation of study treatment.

Treatment compliance with study medication over the study period will be summarized. Compliance will be calculated by counting the days where study drug was administered "As per protocol" according to the records on the Dosage Administration Record (DAR) Summary eCRF. The percentage of days divided by the days of exposure will be analyzed. Compliance will be categorized into < 80% and 80% - 100% and summarized for the Safety Set.

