2.5.1 Primary endpoint

The primary variable is the number and percentage of patients who reported treatment emergent adverse events during the 52 week study period for the Safety set.

All treatment emergent adverse events including asthma exacerbations will be summarized and listed. Adverse events starting on or after the time of the first inhalation of study drug but not later than 7 days (30 days in the case of a SAE) after the last administration will be classified as a treatment emergent adverse event. Any adverse events that started during the study before the time of the first inhalation of study drug will be classified as a prior adverse event.

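### The adverse-event table by time at onset shows crude percentages over windows of nominally 12, 14 and 26 weeks with no patient-time or rate per window, so its columns cannot be compared directly as a time trend.

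*SAP*

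**What the plan says.** SAP 2.5.2 introduces its list of adverse event tables with this sentence: "The number and percentage of patients who reported treatment emergent adverse events will be summarized by primary system organ class, preferred term for". One item in the list is "All adverse events by time at onset", split at Weeks 12 and 26 with the last window open-ended. The Safety Set is the only population named for these tables. The list in Protocol 9.4.2 has no onset-window table, so the SAP adds it.

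Three other provisions bear on how the table reads:

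- **End of the last window.** Protocol 5.5.4 puts the last dose on Day 365. SAP 2.5.1 counts an event as treatment-emergent if it starts after the first inhalation "but not later than 7 days (30 days in the case of a SAE) after the last administration".
- **Exposure.** Under SAP 2.4.1 "the duration of exposure will be summarized with total patient years", once for the whole study. Patients are also counted in exposure bins that include "30 - 86 days, 87 - 183 days, 184 - 254 days".
- **Rates.** SAP 2.5.2 plans "the time to event and the annual rate of events" for serious asthma outcomes only. No such rate is planned for adverse events in general or by window.

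**The concern.** The purpose of a time-at-onset table is to show whether events accumulate, fade or stay level. Here the last window is more than twice as long as the first, so its percentage is larger even if nothing changes over time. A real late decline can be hidden for the same reason. The study exists to supply one-year safety data, so the period after Week 26 is where it adds most, and that column is the one most affected by window length.

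**Working it through.** **The plan's own figures.** The documents give no calculation for this table. The sample size reproduces: 100 − 41 = 59 completers; 59/0.90 = 65.6, so 66 treated; 66/0.75 = 88 screened.

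**Window lengths.** 12, 26 − 12 = 14, and 52 − 26 = 26 weeks. With the treatment-emergent tail, a completer's last window runs (365 + 7)/7 − 26 = 27.1 weeks for non-serious events and (365 + 30)/7 − 26 = 30.4 weeks for serious ones. Patients who stop early contribute less.

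**Inputs.** From the documents: 66 patients and 10% dropout. Assumed: dropout uniform over 52 weeks, S(t) = 1 − 0.1t/52; rates r of 0.05 to 2 per patient-year; the full Safety Set as denominator; each patient counted once per window; tail ignored.

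**Patient-years.** For window a to b: (66/52) × [(b − a) − 0.1(b² − a²)/104].

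- First: (66/52) × (12 − 0.138) = 15.1
- Second: (66/52) × (14 − 0.512) = 17.1
- Third: (66/52) × (26 − 1.95) = 30.5
- Total: 62.7

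**Crude percentage.** For each window, the integral from a to b of (r/52) × exp(−r(t − a)/52) × S(t) dt. The halved case uses r/2 in the last window.

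| Rate per patient-year | Flat rate, % in windows 1/2/3 | Last ÷ first | Halved after Week 26, % |
|---|---|---|---|
| 0.05 | 1.1/1.3/2.3 | 2.01 | |
| 0.1 | 2.3/2.6/4.5 | 2.00 | 2.3/2.6/2.3 |
| 0.2 | 4.5/5.1/8.8 | 1.98 | |
| 0.5 | 10.8/12.1/20.5 | 1.90 | |
| 1 | 20.4/22.8/36.5 | 1.79 | 20.4/22.8/20.5 |
| 2 | 36.6/40.2/58.7 | 1.61 | |

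Ignoring dropout, equal percentages in the first and last windows imply a late rate 12/26 = 0.46 of the early one.

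**Sensitivity.** Exponential dropout gives 20.3/22.7/36.3% at a rate of 1. Adding the 7-day tail moves the last figure to 37.4%. SAP 2.5.2 says "If a patient reported more than one adverse event with the same preferred term, the adverse event will be counted only once" but does not say how that works across windows. If only a patient's first onset counted, the last window at 0.1 would be 4.3% instead of 4.5%. Under that rule the last window falls below the first only above about 68% 52-week incidence, which is plausible at most for the any-AE total.

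**On a rate scale.** Events over patient-years recover 10/10/10 per 100 patient-years for a flat 0.1, and 10/10/5 when it halves.

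**Precision with 66 patients** (exact Poisson 95% limits, expected events rounded):

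- Flat 0.1, events 2/2/3: 13.3 (1.6–48.0), 11.7 (1.4–42.2), 9.8 (2.0–28.7).
- Rate 1 halved, 15 events in each of the first and last windows: 100 (56–164) against 49 (28–81); the intervals overlap.
- Flat 2, events 30/34/61: 199 (134–285), 199 (138–278), 200 (153–257).

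A conditional exact binomial comparison of the first and last windows (two-sided 5%, Poisson counts) detects a true halving with probability about 7%, 25%, 45% and 74% at 0.1, 0.5, 1 and 2 per patient-year.

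**The case against.** The strongest reply is that nothing in the table is wrong. The window bounds are printed, each percentage is a valid incidence for its period, and no document says the columns are to be read as rates. The table is descriptive and single-arm, with no test or decision attached. All of that stands.

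The denominators can also nearly be recovered. Under the dropout assumed above, 10% of 66 is 6.6 leavers, of whom 6.6 × 29/364 = 0.5, 6.6 × 57/364 = 1.0 and 6.6 × 97/364 = 1.8 fall in the first three exposure bins. Placing each group at the earliest or latest day of its bin, and subtracting from the 62.7 total, recovers each window's patient-years to within about 1.5%. This stands for uncommon rows: 66 × percentage ÷ patient-years gives 9.9/9.9/9.8 per 100 patient-years at a flat 0.1. It fails for very frequent rows. At a flat rate of 2 the same division gives 160/155/127, an apparent fall, because a patient with several events in a window counts once. The any-AE row therefore needs event counts, which the planned summary does not give.

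The initial submission uses data cut at each patient's Week 26 visit (SAP 2.13). The last window is then nearly empty, and the other two differ by only two weeks. This also stands; the issue belongs to the final table.

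Finally, rates will not resolve most rows, as the detection probabilities show. That limits the gain but does not remove it, since a rate no longer has window length built into it.

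**Conclusion.** The point holds as a low-cost improvement to one descriptive table. At a constant rate the last column reads about 1.6 to 2.0 times the first, and a halving after Week 26 reads as level. The size rests on assumed event rates, uniform dropout, no tail and counting once per window. The direction follows from the window lengths and does not depend on the dropout shape; it could reverse only for a very frequent row under first-onset-only counting.

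A reader might infer more than the documents support:

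- **That the table is erroneous or the primary result is distorted.** It is not. The primary variable is overall incidence over the study, and no error rate or sample size depends on this table.
- **That the interim submission carries the distortion.** It essentially does not.
- **That adding rates would reveal time trends by system organ class or preferred term.** With 66 patients this is not shown, and no gain is claimed for uncommon rows.

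**What to change.** In SAP 2.5.2, for the onset-window table:

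1. Put the patient-years of exposure in each window's column header.
2. On the any-AE row, give one exposure-adjusted rate per 100 patient-years for each window, defined as all events with onset in the window divided by exposure in that window, with an exact Poisson 95% interval. State that the once-only rule applies to patient counts and not to this event count.
3. Put the 7- or 30-day tail in both numerator and denominator, or in neither.

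Rates on system organ class rows are optional.

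The cost is a few lines of SAP text and a wider table. Dosing dates and event onset dates are already collected. Precision stays limited. The Poisson interval treats events as independent, so it will be too narrow if a few patients contribute many events; a footnote should say so.

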2.5.3 Handling of missing values/censoring/discontinuations

No imputation will be done for missing data. All available data will be summarized.

2.5.4 Supportive analyses

Adverse events of special interest will also be analyzed for the following selected subgroups:

- Age (18 - < 65years, \geq 65years)
- Sex (male, female)
- Pre-bronchodilator FEV₁ in % of predicted FEV₁ at screening Visit 2 (< 50%, 50% - < 60%, 60% - \leq 85%, > 85%)

2.6 Analysis of secondary efficacy objective(s)

2.6.1 Secondary endpoints

The secondary efficacy measurements (Spirometry, PEF, Rescue medication and ACQ-7) during the study will be summarized for the FAS.

Baseline is defined as the last measurement before first dose of the study drug, unless otherwise specified.

Measurements made after patients discontinue study treatment (off-treatment measures) will not be used for any efficacy evaluation.

2.6.2 Statistical hypothesis, model, and method of analysis

Spirometry

For FEV₁ and FVC, the baseline is defined as the mean of the values taken in the clinic at 45 and 15 min prior to first dose at Visit 101. If one of the -45 and -15 min values is missing (or is not confirmed to be pre-dose) then the remaining non-missing value will be taken as the

baseline. If both values are missing (or not confirmed to be pre-dose), then the last out of the pre-bronchodilator measurements taken at the screening Visits 2 or at unscheduled screening visits will be used as the baseline. If the FEV₁, FVC measurements are missing both on Day 1 and at screening visits, the respective baseline values will be set to missing.

The pre-dose FEV₁ is defined as the mean of the pre-dose 45 and 15 min FEV₁ values. The pre-dose FVC is defined as for the pre-dose FEV₁. If any of the pre-dose 45 and 15 min values contributing to the pre-dose value are collected within 7 days of systemic corticosteroid use, 6 hours of rescue medication use, or actual measurement times are post-dose will be set to missing. If one of the two values is missing (or set to missing) then the remaining non-missing value will be taken as pre-dose value. If both values are missing, then pre-dose value will be missing.

The pre-dose FEV₁ and the change from baseline at 12, 26 and 52 weeks of the study treatment will be summarized with descriptive statistics. Summaries will be repeated for pre-dose FVC.

In addition, the means in pre-dose FEV₁ and pre-dose FVC for each visit will be displayed graphically.

Peak Expiratory Flow Rate (PEF)

PEF(liters/min) will be analysed separately for morning and evening values.

The baseline values are defined as the average from all non-missing records taken in the screening period for 14 days before Day 1 administration (in case they were measured before the first intake of study drug as scheduled in the study protocol). When calculating the baseline value there is no limitation to the 14 days immediately prior to Day 1 administration. If a patient has less than 7 days with non-missing data, then the respective baseline value will be set to missing.

The post-baseline measurements start with the morning recordings at Day 2 and end with the evening recordings at the day of last dose. Similar calculations as for baseline data will be done. For the first 26 weeks and the whole 52 weeks, summary values will only be calculated if a patient has at least 30% of their diary days and at least 20 diary days with evaluable data for that variable in the period of interest. For 4-week intervals (defined as 28 days), summary values will only be calculated if a patient has at least 50% of their diary days (i.e. 14 days) of non-missing data. If there will be less than 14 days with data in a 4-week period, then the data should collapse with the previous 4-week interval. The mean morning/evening PEF and the mean change from baseline will be summarized for the first 26 weeks (defined as up to Visit 107), and for the whole 52 weeks of treatment period (defined as up to Visit 111), and will be summarized by 4 weekly interval.

Rescue medication

The total number of puffs of rescue medication per day over the first 26 weeks and over the 52 weeks will be calculated and divided by the total number of days to derive the mean daily number of puffs of rescue medication taken for the patient.

The baseline and post-baseline values are defined in the same way as for the PEF.

The mean daily number of puffs of rescue medication use will be calculated for each patient over the first 26 weeks of treatment period, over the whole 52 weeks of treatment period and over the screening period (which will be used as the baseline value) as described for the PEF. This will be done separately for morning (night-time), evening (daytime), and daily (night-time plus daytime) rescue medication use. If for the value over the whole day (24 hours) the number of puffs is missing for part of the day (either day-time or night-time) then a half day will be used in the denominator to calculate the average value. Any values > 30 for the number of puffs of rescue medication in a 12 hour period will be set to missing. These high numbers are not realistic and could impact the analyses. Where the number of puffs of rescue medication is missing but the rest of the e-diary has non-missing data, the number of puffs will be assumed to be zero.

The mean daily number of puffs of rescue medication use over the first 26 weeks and over the 52 weeks of treatment and the mean change from baseline will be summarized.

In addition, the mean number of puffs of rescue medication in the morning and in the evening, and the percentage of 'rescue medication free days' (defined as any day where the patient did not use any puffs of rescue medication during daytime and night-time) will be summarized.

Asthma Control Questionnaire 7 (ACQ-7)

The baseline value is defined as the score obtained at Day 1. If the value is missing, the last measurements from screening visit 2 or unscheduled screening visits will be used.

ACQ-7 and the change from baseline at 12, 26 and 52 weeks of the study treatment will be summarized.

The proportion of patients who achieve an improvement of at least 0.5 in ACQ-7 (i.e., a decrease of ACQ-7 score of at least 0.5 from baseline) at 26 and 52 weeks visits will be summarized.

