#### **5.5.6 Rescue medication**

At Visit 1, all patients will be provided with a SABA (100 µg salbutamol via pMDI) which they will be instructed to use throughout the screening and treatment epoch as rescue medication on an 'as needed' basis. Patients will be advised that between visits they can take their rescue medication for symptoms. The rescue salbutamol will be provided to the patients by the investigator site and reimbursed locally by Novartis or supplied to the investigator sites locally by Novartis. Nebulized salbutamol is not allowed as rescue medication and use of spacer for rescue medication is not allowed at any time throughout the study.

In order to standardize measurements, patients will be instructed to abstain from taking rescue salbutamol within 6 hours of the start of each spirometry visit unless absolutely necessary. If

rescue medication is taken within 6 hours prior to spirometry assessments, then the visit should be rescheduled to the next day if possible.

Bronchodilator medications that the patients used prior to Visit 1 must be recorded in the asthma-related prior/concurrent medication page of the eCRF, with the stop date for these bronchodilators recorded as the date of Visit 1. The rescue salbutamol provided at Visit 1 for use during the study should NOT be recorded on the asthma-related prior/concurrent medication page of the eCRF. From Visit 1, daily use of rescue medication (number of puffs taken in the previous 12 hours) will be recorded each morning and evening throughout the 52 week treatment epoch by the patient using their electronic diary.

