## **6 Visit schedule and assessments**

[figure not shown]
Table 6-1 lists all of the assessments and indicates with an “x” when the visits are performed.

Patients must be seen for all visits on the designated day, or as close to it as possible. Missed or rescheduled visits should not lead to automatic discontinuation. Patients/subjects who prematurely discontinue the study for any reason should be scheduled for a visit as soon as possible, at which time all of the assessments listed for the final visit will be performed. At this final visit, all dispensed investigational product should be reconciled and the adverse event and concomitant medications reconciled on the CRF.

Patients will be contacted for safety evaluations during the 30 days following the last administration of study treatment.

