### **Spirometry**

Spirometry measurements taken within 7 days of systemic corticosteroid use and/or 6 hours of rescue use will be set to missing and not be imputed, unless specified otherwise.

For FEV1 and FVC, the baseline is defined as the mean of the values taken in the clinic at 45 and 15 min prior to first dose at Visit 101.

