### 13.4 Appendix 4: Patient Asthma Control e-Diary

The following information will be captured:

In the MORNING	In the EVENING
Peak expiratory flow rate	
How did you sleep last night?	
Did you have asthma symptoms upon awakening in the morning?	
Number of puffs of rescue medication during the past 12 hours	
	Peak expiratory flow
	Did your respiratory symptoms stop you from performing your usual daily activities?
	How severe was your shortness of breath today?
	How was your wheeze during the past 12 hours?
	How was your cough during the past 12 hours?
	Did you have Chest tightness during the past 12 hours?
	Number of puffs of rescue medication during the past 12 hours

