2.7.3 Other safety data	18
2.8 Pharmacokinetic endpoints.....	20
2.9 PD and PK/PD analyses	20
2.10 Patient-reported outcomes	20
2.11 Biomarkers.....	20
2.12 [REDACTED].....	20
2.13 Interim analysis.....	21

3	Sample size calculation	21
4	Change to protocol specified analyses	22
5	Appendix	22
5.1	Imputation rules	22
5.2	AEs coding/grading	22
5.3	Laboratory parameters derivations	22
	Direction of interest and definition of clinically notable values	22
5.4	Statistical models	24
5.4.1	Primary analysis	24
5.4.2	Key secondary analysis	24
5.5	Rule of exclusion criteria of analysis sets.....	24
6	Reference	25

List of abbreviations

AE	Adverse event
ATC	Anatomical Therapeutic Classification
AUC	Area Under the Curve
bid	bis in diem/twice a day
CSR	Clinical Study report
CTC	Common Toxicity Criteria
CTCAE	Common Terminology Criteria for Adverse Events
DMC	Data Monitoring Committee
FAS	Full Analysis Set
eCRF	Electronic Case Report Form
IVR	Interactive Voice Response
IWR	Interactive Web Response
MedDRA	Medical Dictionary for Drug Regulatory Affairs
NCI	National Cancer Institute
o.d.	Once Daily
OS	Overall Survival
PFS	Progression-Free Survival
PK	Pharmacokinetics
PPS	Per-Protocol Set
PRO	Patient-reported Outcomes
qd	Qua'que di'e / once a day
QoL	Quality of Life
RAP	Report and Analysis Process
RECIST	Response Evaluation Criteria in Solid Tumors
SAP	Statistical Analysis Plan
SOC	System Organ Class
TFLs	Tables, Figures, Listings
WHO	World Health Organization

1 Introduction

This document contains details of the statistical methods that will be used in the phase III clinical trial CQVM149B1305. This study is designed to provide long term safety data of QMF149 in Japanese patients with asthma for the registration of QMF149 in Japan.

Data will be analyzed according to Section 9 of the study protocol.

Important information and details are given in the following sections.

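### The SAP baseline rule for FEV1 omits the rescue and corticosteroid exclusions that the protocol applies to all spirometry, and no databased source is named for the time of last salbutamol use

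*SAP*

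**What the plan says.** **Protocol rule.** Under Spirometry, Protocol 9.5.1 states: "Spirometry measurements taken within 7 days of systemic corticosteroid use and/or 6 hours of rescue use will be set to missing". Such values are not imputed. The sentence is not limited to post-baseline visits, but it yields to any other specification.

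**SAP rule.** SAP 2.6.2 handles FEV1 and FVC in two paragraphs.
- Baseline is the mean of the two pre-dose readings at Visit 101. The handling begins: "If one of the -45 and -15 min values is missing (or is not confirmed to be pre-dose". In that case the other reading is used. If both fail, "then the last out of the pre-bronchodilator measurements taken at the screening Visits 2 or at unscheduled screening visits will be used as the baseline".
- The pre-dose value is defined in the next paragraph. Only there do the corticosteroid and rescue triggers appear, ending "6 hours of rescue medication use, or actual measurement times are post-dose will be set to missing".

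SAP section 4 reports no change from the protocol's analyses.

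**Rescue data.** The e-diary item in Protocol Appendix 4, asked morning and evening, is "Number of puffs of rescue medication during the past 12 hours". Protocol 5.5.6 adds: "The rescue salbutamol provided at Visit 1 for use during the study should NOT be recorded on the asthma-related prior/concurrent medication page". Protocol section 6 says that "Table 6-1 lists all of the assessments", and no row there is for the time of last rescue use.

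**The concern.** Change from baseline in pre-dose FEV1 at Weeks 26 and 52 is a secondary endpoint. With no control arm, an error in baseline passes straight into the reported mean change. A reading taken soon after salbutamol is too high: at baseline it shrinks the apparent improvement, and at Week 26 or 52 it enlarges it. The 6-hour rule is the analysis-stage protection against both.

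That protection has two weak points. The SAP's own baseline rule does not carry it, so two programmers could derive different baselines from the same data. And the rule needs the time of last use, while the documents describe only a count. Week 26 results also feed the interim analysis for the Japanese submission (Protocol 9.7), so the first reported figures would be affected.

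**Working it through.** The plan gives no figure on this point to reproduce. The check sets the rules side by side and then illustrates the possible size.

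**1. Triggers for dropping a reading**

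| Trigger | Protocol 9.5.1, all spirometry | SAP 2.6.2, pre-dose value | SAP 2.6.2, Visit 101 baseline |
|---|---|---|---|
| Missing | not stated | yes | yes |
| Post-dose or not confirmed pre-dose | not stated | yes | yes |
| Within 6 h of rescue | yes | yes | not stated |
| Within 7 days of systemic corticosteroid | yes | yes | not stated |

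At baseline the rescue trigger matters more. Table 5-1 requires oral or parenteral corticosteroids to have stopped 4 weeks before Visit 1, and exclusion criterion 6 sends patients with a steroid-treated exacerbation during screening to re-screening.

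**2. What a 12-hour count can show.** A recorded zero that covers the period up to spirometry rules out use in the last 6 hours. A positive count does not place the use. Assume k separate occasions, each independent and uniform over the 12 hours. The chance that at least one fell in the last 6 hours is 1 − 0.5^k:
- k = 1: 50%
- k = 2: 75%
- k = 3: 87.5%

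SAP 2.6.2 also sets a missing count to zero when the rest of the diary is complete. That serves the rescue endpoint and does not show that none was used.

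**3. One use usually spoils both baseline readings.** The readings are 45 − 15 = 30 minutes apart. Use less than 5.5 hours before the −45 min reading lies within 6 hours of both. For most affected patients the fallback would therefore be Visit 2, not the other Day 1 reading.

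**4. Illustrative size.** Let E be the bronchodilator effect on a contaminated reading, and f_base and f_post the shares of patients affected at each time.

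Shift in mean change = E × (f_post − f_base)

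Both inputs are assumptions. E = 100-200 mL takes half to all of the 200 mL reversibility threshold as a scale. f_base = 5-20% has no source in the documents; of 66 patients it is 3.3 to 13.2.

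| E | f_base | f_post = 0 | f_post = f_base/2 | f_post = f_base |
|---|---|---|---|---|
| 100 mL | 5% | −5 mL | −2.5 mL | 0 |
| 100 mL | 20% | −20 mL | −10 mL | 0 |
| 200 mL | 5% | −10 mL | −5 mL | 0 |
| 200 mL | 20% | −40 mL | −20 mL | 0 |

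The column f_post = 0 is the literal SAP reading with post-baseline values fully cleaned. If timing is not available, those values are not fully cleaned either and the shift moves to the right-hand columns. If f_post exceeded f_base, the sign would reverse.

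**The case against.** **The protocol already covers baseline.** The SAP introduction says "Data will be analyzed according to Section 9 of the study protocol", and section 4 declares no change. A Visit 101 reading set to missing under Protocol 9.5.1 is then missing under the SAP baseline rule, and the fallback applies. Protocol 6.4.1 also defines pre-dose FEV1 as the mean of the two readings before the evening dose at the site, which Visit 101 has. This is a fair reading, so a reader should not conclude that the plan has removed baseline from the rule. It does not settle the matter: 9.5.1 gives way to other specifications, and a separate SAP baseline rule with its own triggers can be taken as one.

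**The 6-hour rule might look impossible to apply.** The documents do not support that. Recorded zeros resolve part of the data. Sites must learn the timing to apply the abstention and rescheduling instructions in 5.5.6 and Table 5-1. Table 6-1 does not show every collected field: dosing time is collected under 6.3 but has no row of its own. The bar in 5.5.6 concerns one eCRF page, and the source-only row for reviewing rescue use is in Table 5-4, for patients who stop treatment early. What stands is that no databased source for the timing is named and positive counts stay unclassified.

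**Bronchodilated values might be thought certain to remain.** They may remain. Tables 5-1 and 5-3 require salbutamol to be withheld for 6 hours. Section 5.5.6 allows use when absolutely necessary and asks for rescheduling where possible, while the Table 5-1 footnote makes rescheduling optional. These safeguards lower the chance without removing it.

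**The size is assumed.** This stands. Not every patient has shown a 200 mL response at Visit 2, because historical reversibility or bronchoprovocation also qualifies.

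**Conclusion.** The point holds as an inconsistency to reconcile and a data source to name. SAP 2.6.2 states the rescue and corticosteroid triggers for the pre-dose value and not for baseline, Protocol 9.5.1 states them for all spirometry, and the SAP declares no change. Read literally, the result is asymmetric cleaning, which biases the change in FEV1 towards a smaller improvement.

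The likely size cannot be derived, because the documents give no share of affected readings. The 5-40 mL understatement rests on three assumptions: 5-20% of baselines affected, an effect of 100-200 mL, and clean post-baseline values. With equal shares at both times the average shift is zero.

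The consequence is limited. The endpoint is secondary, summarized descriptively and not tested, and the primary adverse-event variable does not use spirometry. The correction is cheap enough to be worth making before database lock.

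**What to change.** 1. **SAP 2.6.2, baseline paragraph.** Change the trigger to: *missing, not confirmed to be pre-dose, or taken within 6 hours of rescue use or 7 days of systemic corticosteroid use*. Keep the existing fallback to the other reading or to screening, and apply the same triggers to the fallback value.

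2. **Source of timing.** At Visits 2, 101, 104, 107 and 111, record the date and time of last salbutamol use before spirometry, or a yes/no for use within 6 hours. If such a field exists, name it. State that the 6-hour rule uses it. The early-discontinuation visit need not be included for this endpoint: SAP 2.1.1 lists those data, and 2.6.1 excludes off-treatment measures from efficacy.

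3. **Unresolved cases.** State how a positive 12-hour count without a time is handled, and that a missing count set to zero is not evidence of no use.

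The cost is one SAP clause, a short handling rule and at most one data item at visits already planned. The downside is that a few baselines will rest on one reading or on Visit 2, about two weeks before the first dose. Reporting how many do so would let readers judge the effect.
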